**Clinical Observation Of The Gynecological
Iron-Deficiency Anemia Treated With
Buxue Yimu Pills**

Version 2 (June,2017)

CONTENTS

A. OBJECT

B. STUDY METHOD AND DESIGN

C. TECHNICAL ROUTE

D. STATISTICS ANALYSIS

E. QUALITY CONTROL MEASUREMENT AND RESULT

PUBLICATION

F. SOURCE(S) OF FUNDING

A. OBJECT

Buxue Yimu Pills, Ferrous Sulfate each improve anemia, but they do so by different mechanisms. We generally treat patients with uncomplicated Iron Deficiency Anemia with oral iron due to the ease of administration, and Ferrous Sulfate is one of the most commonly used drugs.

Buxue Yimu Pills consists of multiple Chinese herbs including Angelica Sinensis, Astragalus, Donkey-Hide Gelatin, Herba Leonuri, Citrus etc., which gains widespread application in the treatment after women's abortion or operations of uterine cavity.

This study evaluates Buxue Yimu Pills, Ferrous Sulfate and the addition of Buxue Yimu Pills to Ferrous Sulfate in the treatment of Iron-Deficiency Anemia in adult women, with the object to perform clinical efficacy and safety assessment. In addition, we expect to conduct research on its pharmacodynamics, trying to probe into the mechanism and pharmacodynamic material basis of this mysterious traditional Chinese medicine.

B. STUDY DESIGN AND METHOD

— **STUDY DESIGN:** 180 women with mild to moderate Iron Deficiency Anemia were observed in a prospective multi-center randomized controlled clinical trial.

Inclusion Criteria:

1. Subject is a female between the age of 18 and 50.
2. Subject suffers from mild to moderate anemia with a hemoglobin between 80g/L and 110 g/L.
3. Subject has definite gynecological etiological factors of iron deficiency
4. Subject provides written informed consent.

Exclusion Criteria:

1. Subject underwent chronic digestive tract inflammation, uncontrolled digestive or urinary system bleeding.
2. Subject has other complications in addition to gynecological diseases leading to iron deficiency, such as hemorrhagic diseases of hematologic system, parasitic diseases like ancylostomiasis, chronic intravascular hemolysis, mechanical hemolysis like prosthetic valve, renal dysfunction and hemodialysis.
3. Subject is pregnant or lactating.
4. Subject has a severe systemic disease, such as cardiovascular system
5. Subject has a history of malignancy or radiotherapy.
6. Subject has undergone any Iron deficiency anemia treatment including Iron supplements or blood transfusion within 1 month prior to randomization.

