7. Subject has mental disorder incapable of elementary cooperations.
8. Subject has participated in other clinical researches of medicine within 1 month prior to randomization.

—**METHODS:** The participants were divided randomly into 3 groups:

- a. Experimental group1(60 patients): Buxue Yimu Pills 12g pill by mouth, twice daily.
- b. Experimental group2(60 patients): Buxue Yimu Pills 12g pill by mouth, twice daily and Ferrous Sulfate 0.3g tablet by mouth, three times daily.
- c. Active Comparator group (60 patients): Ferrous Sulfate 0.3g tablet by mouth, three times daily.

—**TREATMENT PERIOD:** 1month.

—**OUTCOMES MEASUREMENT :**

Primary Outcome (Anemia Related Assessment, Clinical Efficacy Assessment): Complete Blood Count, Urine Routine, Reticulocyte Count, Iron Metabolism index (Serum Iron, Total Iron Binding Capacity, Serum Ferritin), Coagulation Indexes (Activated Partial Thromboplastin Time, APTT), Prothrombin Time (PT), Fibrinogen (FIB), Thrombin Time(TT), The Short Form-36 Health Survey (Sf-36).

Secondary Outcome (Safety Assessment): Hepatic Function, Renal Function, Blood Glucose, Electrolyte Semiconductor Junction, Electrocardiogram(ECG)

Other Pre-Specified Outcome (Metabonomics Assessment): Build up a new therapeutic evaluation system about Buxue Yimu Pills in the treatment of Gynecological Iron-Deficiency Anemia, which integrating clinical information with metabonomics, to probe into the mechanism and pharmacodynamic material basis of this mysterious traditional Chinese medicine.

C. TECHNICAL ROUTE

Screening Period (Day -30~0)

1. We enrolled in-patients according to the uniform inclusion/ exclusion criteria above, and informed consent will be signed by all study participants before joining in the study.
2. Collect medical history and certain demographic features of every participant, and perform general physical examination as well as gynecologic physical examination.
3. Complete outcomes measurement above.
4. Make the appointment for the follow-up.

The First Follow-Up Period (Day -30~0)

1. Group randomly and distribute medicine and patient diary pamphlet.
2. Inform application notice.
3. Make the appointment for the next follow-up.

The Second Follow-Up Period(Day0~30)

1. Collect medical history and certain demographic features of every participant, and perform general physical examination as well as gynecologic physical examination, again.
2. Complete outcomes re-measurement above.

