3. Take back the medicine and patient diary pamphlet.

D. STATISTICS ANALYSIS

Data was analyzed using SPSS Version 18. All quantitative informations are expressed as mean values \pm standard deviation (SD). Statistical significance was assessed using unpaired Student's t-test or chi-square test. Probability values of less than 0.05 were considered significant and an asterisk identifies such significance in the figures. We will also compare the adverse effect of each group using descriptive statistics.

E. QUALITY CONTROL MEASUREMENT AND RESULT PUBLICATION

1. Every center of the research possesses the competence of scientific research to conduct clinical studies. Special people from each center will be put in charge of the research and monitoring the whole procedure. The rights and interests, responsibility and obligation of all centers will be standardized with the research agreement.
2. The maintenance, secrecy and safety of data and informations will be guaranteed by Department of Obstetrics and Gynecology, Peking Union Medical College Hospital.
3. Every center is responsible to subject enrollment and finish the prospective follow up.
4. The researchers' findings will be released in a paper published online.

F. SOURCE(S) OF FUNDING

1. This study does not charge any fee to any patients.
2. All the investigational drugs and cost of the study are provided by Qian Jin Pharmaceutical CO., LTD.

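### Every listed source of adverse-effect information after randomization depends on one final visit, and stopping for side effects is not counted by arm, so the safety comparison may miss harm

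*Combined protocol and SAP*

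**What the plan says.** Section A (Object) names clinical efficacy and safety assessment as the aim for the three regimens. Section B, under Outcomes Measurement, defines safety as follows: "Secondary Outcome (Safety Assessment): Hepatic Function, Renal Function, Blood Glucose", and the list then ends with electrolytes and ECG. Neither adverse effects nor stopping study medicine is on it.

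Section C (Technical Route) gives the contacts. At the First Follow-Up the instruction is: "Group randomly and distribute medicine and patient diary pamphlet". At the Second Follow-Up, history and examination are repeated, the outcomes are measured again, and the last instruction is: "Take back the medicine and patient diary pamphlet". Nothing is listed between the two.

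Section D (Statistics Analysis) says of harms only: "We will also compare the adverse effect of each group using descriptive statistics". It names no data source, no denominator and no handling of women who stop early. Section E adds a general duty: "Every center is responsible to subject enrollment and finish the prospective follow up".

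**The concern.** The trial compares a herbal product alone, oral iron alone, and the two together. Tolerability is an obvious question in that design, above all for the combination, and stopping because of side effects is a direct measure of it. The plan does not collect that measure as an outcome.

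The sources it does list all share one point of failure. If a woman stops because she feels unwell and does not come to the Second Follow-Up, her diary, history, examination, laboratory values and ECG are lost together. Because Section D fixes no denominator, she could also drop out of the table without trace. A reader of the final report could not tell whether a low adverse-effect rate reflects good tolerability or the absence of the women who tolerated treatment badly.

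**Working it through.** **Step 1: where information can come from after randomization (Section C).**

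| Source | When obtained | Available if she misses the Second Follow-Up? |
|---|---|---|
| Diary | Handed out at First Follow-Up, collected at Second | No |
| Returned medicine | Second Follow-Up | No |
| History and examination | Second Follow-Up | No |
| Laboratory tests, ECG | Screening and Second Follow-Up | No value after treatment |

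The Second Follow-Up is given as a period, Day 0 to 30. I read it as one visit, because it has one set of procedures and ends with the medicine being taken back.

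**Step 2: what is counted.** Even if every woman who stops does return, no listed outcome separates one who stopped after a few days from one who finished the month. This part of the point needs no assumption about attendance.

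**Step 3: how large the effect could be.** The plan gives no adverse-effect rate, dropout rate or denominator, so there is no figure of its own to reproduce. The only number taken from it is 60 women per arm (3 × 60 = 180). All other counts below are assumptions.

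Let *a* be the women in an arm with an adverse effect and *m* those of them who stop and are not seen. If only women seen at the final visit are tabulated and no unaffected woman is lost:

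rate shown = (*a* − *m*) / (60 − *m*)

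One arm:
- *a* = 20, *m* = 10: 10/50 = 20.0%, against a true 20/60 = 33.3%.
- *a* = 12, *m* = 6: 6/54 = 11.1%, against a true 12/60 = 20.0%.
- *m* = 0 (women who stop still attend): the rate shown equals the true rate.

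Two arms, X and Y (differences X − Y in percentage points, from unrounded rates):

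| True X v Y | *m* in X, Y | Shown X v Y | Difference shown | True difference |
|---|---|---|---|---|
| 18/60 v 6/60 | 0, 0 | 30.0% v 10.0% | 20.0 | 20.0 |
| 18/60 v 6/60 | 6, 2 | 12/54 = 22.2% v 4/58 = 6.9% | 15.3 | 20.0 |
| 18/60 v 6/60 | 9, 3 | 9/51 = 17.6% v 3/57 = 5.3% | 12.4 | 20.0 |
| 18/60 v 6/60 | 9, 0 | 17.6% v 10.0% | 7.6 | 20.0 |
| 18/60 v 18/60 | 6, 0 | 22.2% v 30.0% | −7.8 | 0 |
| 18/60 v 18/60 | 9, 0 | 17.6% v 30.0% | −12.4 | 0 |

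**Step 4: direction.** Treat the two one-arm examples as two arms. The difference falls from 33.3 − 20.0 = 13.3 points to 20.0 − 11.1 = 8.9 points, but the ratio rises from 33.3/20.0 = 1.67 to 20.0/11.1 = 1.80. If only the first arm loses women, both arms show 20% (10/50 and 12/60) and the difference disappears. In the last two rows of the table, loss in one arm creates a difference where none exists. The direction therefore depends on the pattern of loss and on the scale used.

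**Step 5: the denominator alone does not repair this.** With *a* = 20 and *m* = 10, dividing by all 60 gives 10/60 = 16.7%, further from 33.3% than the 20.0% among women seen. The missing information has to be sought, and what remains missing has to be reported.

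**The case against.** A reader might infer that the women who quit because of harm are the ones absent from the comparison, and that the arms will therefore look more alike in safety than they are. The documents do not support either statement.

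- They do not say what the diary records, or that it is the source of adverse-effect data.
- They do not say that a woman who stops her medicine skips the final visit. Stopping treatment is not the same as leaving follow-up. The Second Follow-Up is booked in advance, its history and examination are not limited to women still on treatment, and the returned medicine could reveal early stopping.
- Centers are charged with completing follow-up, and Section E mentions a research agreement on their responsibilities that is not part of these documents.
- The examples in the working assume that a third or a half of affected women are lost and no unaffected woman is. Nothing in the plan supports those shares.
- Descriptive reporting of adverse effects at 60 per arm is an ordinary choice.

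All of this stands against a claim of demonstrated bias. It does not close the gap. The repeated history and the returned medicine depend on the same visit as the diary. The duty on centers assigns responsibility but gives no procedure for a woman who stops or does not come. None of these points adds a count of stopping by arm or a denominator.

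**Conclusion.** The concern holds as a gap in capture and reporting, not as a proven bias. As written, the plan does not count stopping for side effects by arm, states no denominator for adverse effects, and obtains all its listed information after randomization at one visit. A woman who stops because of side effects and does not return would contribute nothing to the comparison in Section D.

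The effect ranges from none, if women who stop still attend, to a substantial distortion. In the assumed examples, 33% is shown as 20% in one arm, a true difference of 20 points is shown as 7.6, and a false difference of up to 12.4 points appears between equal arms. These figures assume 60 women per arm, tabulation of attenders only, and loss confined to affected women. The documents do not place the trial within that range or fix the direction. The change is worth making because safety is a stated object and the remedy is cheap.

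**What to change.** 1. **Section B, safety outcomes.** Add the number and percentage of women in each arm who stopped study medicine, with the reason, showing stopping for an adverse effect separately.
2. **Section C.** When a woman stops study medicine or misses the Second Follow-Up, the center telephones her, records any adverse effects and arranges for the diary to be returned.
3. **Section D.** Use all women given study medicine in each arm as the denominator for adverse effects, and state for each arm how many have no adverse-effect information. The analysis can remain descriptive.

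The cost is a few telephone calls, one item on the case report form and one table. Adverse-effect rates may look higher than they would have otherwise. No dose, schedule or treatment rule changes.
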